#### **3.3 Investigational Device**

The 'HeraBEAT USATM (HeraBEATTM) is a wireless Smart Fetal Ultrasound Doppler measuring device designed to be self-administered by pregnant women. The 'HeraBEATTM' device safety and performance claims allow continuous and accurate measurement of fetal heart rate (FHR) and maternal heart rate (MHR) throughout the pregnancy starting at 12 weeks gestation. This study shall evaluate the device performance starting at 20 weeks gestation.

Technologically, HeraBEATTM is similar to other FHR devices currently on the market in terms of device usage but differ by design in its interface. The HeraBEATTM device uses a smartphone-based interface, with real time instructions for localizing FHR. The device also measures the maternal heart rate (MHR) and uses this in its algorithm. This is primarily in order to overcome common lay person usage errors such as confusion between MHR and FHR or difficulties locating the FHR due to lack of experience. The data obtained from the device is uploaded to a secure HIPAA compliant cloud-based server for medical providers to review. The intended use, indication for use and contraindications are similar to current medical grade handheld fetal Doppler devices.

The specifications for the HeraBEATTM are:

- The device will measure fetal heart rate in range of 50-240 BPM.
- The device will measure fetal heart rate with accuracy of  $\pm 2$  BPM.
- The device will measure fetal heart rate with resolution of 1 BPM.
- FHR value is calculated and displayed every 1 second.
- Device measures FHR and MHR starting at 12 week gestation.
- The device will measure maternal heart rate in range of 45-240 BPM.
- The device will measure maternal heart rate with accuracy of  $\pm 2\%$  or 1 BPM, whichever is greater.
- The device will measure maternal heart rate with resolution of 1 BPM.

• MHR value is calculated and displayed every 1 second.

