## 5.6 Schema

Patients will be instructed to monitor their fetus once weekly, using their assigned device, from 20 weeks to 36/37 weeks gestation. Patients using the HeraBEATTM device will have their FHR and MHR data displayed on their App, and uploaded to a HIPPA compliant cloud based server, which can be accessed by the healthcare provider for review (*Appendix B*). Patients using the standard handheld Doppler device will be given a study brochure for recording their weekly data. Patients using the HeraBEATTM device will be instructed to bring their device during their outpatient clinical appointments, for comparison of MHR and FHR during their routine clinic appointments using methods documented in *Appendix E*.

After approximately 8 weeks of monitoring, patients will complete a System Usability Survey (SUS Survey), *Appendix D* to assess ease of use of the device, then crossover to the alternate study product.

Patients who are randomized to HeraBEATTM from 20weeks gestation to 28 weeks gestation will be given the standard fetal Doppler. Patients who are randomized to the standard Fetal Doppler will switch to the HeraBEAT.TM At the conclusion of each patient device use (28 weeks and 36 weeks gestation), participants will complete the System Usability Survey (Appendix D) to assess ease of use of each device.

- 1- Nurse assesses eligibility criteria, ascertains mother's interest, and study coordinator will obtain consent and complete randomization Patients will be given home monitoring equipment after their fetal anatomy sonography is complete, inclusion/exclusion criteria confirmed and Patient Usability Form completed (Appendix C).
- 2- After 8 weeks of use, participants will complete the System Usability Scale (SUS) survey (Appendix D), return the first study device and crossover to the second device. An independent device use assessment (Appendix C) will be assessed by study nursing staff and completed for the second device.
- 3- At the conclusion of 8 weeks of self-monitoring with assigned device, participants will complete the System Usability Scale (SUS) survey to assess ease of use (Appendix D).

Prior to registering study participants, all eligibility criteria will have been met and fully documented. Mothers will be randomized by the study coordinator after completion of standard informed consent for participation in clinical research including permission to use Protected Health information.

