## 5.9.2 Participants Reported Outcomes

System Usability Survey: Ease of use will be evaluated using a survey assessing comfort with use, troubleshooting, ease of obtaining FHR, any safety concerns, and whether or not the device was useful for confirming fetal well-being.

Medical device usage: While mothers are using the standard home Doppler they will be asked to track usage information. These metrics will include date of use, user (mother/partner), estimated time to find FHR, and estimated FHR.

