#### 8.0 Data Analysis Plan

The study will be analyzed according to the intention to treat principle, including all mothers randomized to the study in the arm to which they were randomized, regardless of whether they received the intervention assigned.

Baseline characteristics will be reported in the study results with continuous values being reported as means and standard deviations or median interquartile range as appropriate. Categorical values will be reported as counts and proportion. Two sample t-tests or Wilcoxonrank sum test and chi-squared tests or Fishers exact test will be used as appropriate. Any baseline imbalances (p<0.05) will be explored as a possible confounder to adjust for when the outcome measures are analyzed. We will adhere to the CONSORT guidelines to transparently

report study results and ensure that sufficient information is included to allow for assessment of the study's internal and external validity.

Ease of use will be estimated from the System Usability (SUS) validated questionnaire. These data will be analyzed as a two sample t-test prior to cross over. After cross over we will analyze these data using an ANCOVA adjusting for order of medical devices or as a paired t-test as appropriate.

Within the SUS survey, we will also examine trends within individual questions using chi-square tests. Clinical concerns in FHR will be indicated as a FHR less than 110 bpm or greater than 160 bpm. These data will be analyzed as McNemar's test on the association of the study medical devices with the clinical standard of care. Comparing ease of use metrics will be done using an ANCOVA analysis or generalized estimating equation as appropriate adjusting for gestational age. Additional ad-hoc analysis will be performed using standard techniques appropriate for randomized trials, with each outcome compared between study arms using t-tests for continuous outcomes and chi-square tests for dichotomous outcomes. If there are differences in baseline characteristics between the two study groups, these will be accounted for using ANCOVA or regression models which include an indicator for study arm.

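### Section 8.0 judges clinical concern from FHR alone and leaves HeraBEAT's uploaded MHR unanalysed, so a home reading of the mother's pulse can count as FHR found and, below 110 bpm, as low FHR

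*Combined protocol and SAP*

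**What the plan says.** Section 3.3 (Investigational Device) explains that MHR is measured mainly to overcome "common lay person usage errors such as confusion between MHR and FHR or difficulties locating the FHR due to lack of experience". It adds: "The device also measures the maternal heart rate (MHR) and uses this in its algorithm". Section 5.1 puts success in finding FHR, and the clinical usefulness of the fetal and maternal rate data, into the primary objective. Under section 5.6 both rates go from the app to the server. HeraBEAT users also bring the device to the clinic "for comparison of MHR and FHR during their routine clinic appointments using methods documented in" Appendix E.

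The analysis rule in section 8.0 is: "Clinical concerns in FHR will be indicated as a FHR less than 110 bpm or greater than 160 bpm". The next sentence reads: "These data will be analyzed as McNemar's test on the association of the study medical devices with the clinical standard of care". Section 8.0 does not mention MHR. Section 5.9.3 uses it only to count how often women record readings.

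For the standard Doppler, section 5.9.2 lists what the woman writes down: "These metrics will include date of use, user (mother/partner), estimated time to find FHR, and estimated FHR". Maternal pulse is not on the list.

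**The concern.** If the sensor picks up the maternal pulse, the number recorded as FHR is not fetal. The rule in section 8.0 cannot tell this from a fetal reading. Such a session adds to the FHR-found success that section 5.1 puts in the primary objective. It also enters the concern outcome according to how fast the mother's heart is beating.

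Two results are at stake. The functionality result could include sessions that did not measure the fetus. The low-FHR flag could mix slow fetal rates with maternal signal, with no planned way to separate them. The data for a first check on HeraBEAT are already collected, but no analysis is attached to them.

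**Working it through.** **No planned figure to reproduce.** The documents give no rate of maternal capture, no expected number of flagged readings and no power for this outcome. The 99.7% power in section 8.2 concerns the SUS score and has no bearing here.

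**Tracing one captured home session.** Section 3.3 states: "The device will measure maternal heart rate in range of 45-240 BPM". That range spans all three zones of the rule:
- MHR below 110: counted as FHR found, and as a low-FHR concern.
- MHR 110 to 160: counted as FHR found, and as normal.
- MHR above 160: counted as FHR found, and as a high-FHR concern.

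No step in section 8.0 identifies the session as maternal in any of the three.

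**What the other provisions reach.**
- Observed use on Appendix C (sections 5.5 and 5.6): the clinic session at the start of each device, not home readings.
- Clinic MHR/FHR comparison (section 5.6): HeraBEAT users at appointments, with no analysis of it in section 8.0.
- McNemar's test (section 8.0): paired disagreement with clinical care, not its cause. The pairing unit is not stated.
- Follow-up of abnormal FHR (section 5.7): clinical action, not a statistical classification.

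**Can HeraBEAT data identify candidates?** Stated accuracies (section 3.3): FHR ±2 bpm; MHR ±2% or 1 bpm, whichever is greater. If both channels follow the same heart, they should agree within

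T(m) = 2 + max(0.02 × m, 1), where m is MHR.

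- m = 45: 2 + 1 = 3.0 bpm
- m = 90: 2 + 1.8 = 3.8 bpm
- m = 110: 2 + 2.2 = 4.2 bpm
- m = 150: 2 + 3.0 = 5.0 bpm

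So a check is feasible with values already uploaded.

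**Size, as illustration only.** Sessions per device (sections 5.6 and 8.2): 50 women × 8 weeks = 400, or 45 × 8 = 360 after 10% loss. Assumptions not in the documents: MHR roughly normal with mean 80 to 95 and SD 10 to 15 bpm; capture in 1%, 5% or 10% of sessions.
- Share of captures below 110: Φ((110 − 80)/10) = Φ(3) = 0.999 down to Φ((110 − 95)/15) = Φ(1) = 0.841.
- False low flags = sessions × capture rate × share. At 1%: 360 × 0.01 × 0.841 = 3.0 to 400 × 0.01 × 0.999 = 4.0. At 5%: about 15 to 20. At 10%: about 30 to 40.

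The share of low flags that are maternal depends almost wholly on what is assumed. Take a true low rate of 0.5% (360 × 0.005 = 1.8 sessions) and let every capture read below 110. Capture of 0.1% gives 0.36/(0.36 + 1.8) = 17%; capture of 5% gives 18/(18 + 1.8) = 91%.

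**McNemar's test.** Assume one pair per woman and a normal clinic reading. Expected false-low discordant pairs are 45 × 0.01 × 0.841 = 0.4 to 50 × 0.01 × 0.999 = 0.5 at 1% capture, 1.9 to 2.5 at 5%, and 3.8 to 5.0 at 10%. The exact two-sided test needs six pairs all in one direction for p < 0.05 (2 × 0.5⁶ = 0.031; five pairs give 0.0625). Under these assumptions it would probably miss the error, and it could not name the cause.

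**The case against.** The strongest reply is that the plan does more than the flag suggests. Staff watch unassisted use of both devices and record mistakes, and HeraBEAT is compared with clinic MHR and FHR. McNemar's test against clinical care would show a false low (device low, clinic normal) and a missed low (device normal, clinic low) as discordance in opposite directions. The device algorithm already uses MHR, abnormal readings are followed up clinically, and SUS drives the sample size.

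All of that stands, and it rules out several stronger readings that a reader might infer:
- *Maternal capture is never measured.* The clinic comparison and observed use contradict this. Appendices C and E were not in the text available, so it cannot be said that they omit it.
- *HeraBEAT does misread the maternal pulse as FHR.* The documents show only that a captured reading can be counted this way. The algorithm is meant to make it less likely.
- *Most low flags are maternal artefact.* No capture rate or true low rate is given, and the 17% to 91% range above only restates the assumptions.
- *False lows and missed lows cannot be told apart.* On readings paired with a clinic reference, they can.
- *Adding maternal pulse to the Doppler log would solve the comparison.* A self-counted pulse taken at another moment cannot support a rule of about 4 bpm. An extra task on the comparator alone could lower its SUS score, the outcome named as primary in section 8.2.

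What the reply does not reach is the unsupervised home reading. As described, none of these provisions classifies it against the MHR uploaded with it.

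**Conclusion.** The point holds in a limited form. The concern rule uses FHR alone, section 8.0 attaches no analysis to HeraBEAT's MHR, and a home session that captured the mother's pulse can enter both the success count and the concern flag unrecognised. This follows from the text and needs no assumed rate.

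Its size cannot be estimated from the documents; the counts above are illustrations under stated assumptions. The conclusion about the clinic comparison rests on section 5.6 as written, and Appendix E could narrow it. The SUS comparison and its sample size are unaffected, and the 110/160 limits are not questioned. This is an inexpensive improvement to the functionality and FHR analyses. It would not support a between-device claim about maternal capture.

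**What to change.** In section 8.0:
- Keep the 110/160 flag.
- Define one FHR value and its simultaneous MHR for each HeraBEAT session. Both are computed every second and a session can hold five minutes of successful measurement (5 × 60 = 300 values), so the summary must be fixed in advance.
- Label a session *possible maternal signal* when the two agree within 2 bpm plus the greater of 2% of MHR or 1 bpm, and *unclassifiable* when MHR is missing. Section 5.9.3 allows for readings with FHR only.
- Report the possible-maternal-signal proportion with a 95% CI that allows for repeated sessions per woman, and the number unclassifiable.
- Report FHR-found success and concern flags with and without the labelled sessions.
- Use the clinic FHR/MHR check as the reference for the label. Because the algorithm already uses MHR, coincidence of the two displayed rates may understate capture.
- Keep captured readings as device errors in the main McNemar analysis, and name its pairing unit.
- State as a limitation that maternal capture cannot be identified on the standard Doppler, so no between-device claim about it can be made.

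Cost: a few lines of text and a little more analysis, with no new HeraBEAT data and no added task for participants. The downside is that a true coincidence of FHR and MHR will occasionally be mislabelled, which is why results are shown both ways.

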#### **1.0 Specific Aims**

The coronavirus disease 2019 (COVID-19) global pandemic rapidly changed the standard model of prenatal care in the United States. In response to this pandemic, the Society for Maternal Fetal Medicine (SMFM) and the American College of Obstetricians and Gynecologists (ACOG) recommended integrating telehealth services as appropriate, limiting face-to-face patient contact if clinically possible, and considering alternative methods of providing obstetric care, to decrease the risk of COVID-19 exposure.

Evidence for integrating home monitoring devices and telehealth services for the provision of prenatal care is limited Innovative options for home monitoring of fetal well-being, as a component of virtual or a hybrid prenatal care model is equally negligible. While a few studies have focused on home monitoring of maternal blood pressure, capillary blood glucose, and contraction patterns, few have investigated maternal home monitoring of fetal heart rate, as a component of virtual or hybrid prenatal care.

In addressing this gap, HeraMED designed and tested a medical grade, smartphone fetal heart rate monitor - HeraBEAT USATM ((HeraBEATTM) - for self-administration at home, under clinical guidance of an obstetric provider.

We propose that HeraBEATTM self-administered at home by pregnant women, under clinical guidance, will result in accurate monitoring of fetal heart rate, provide peace of mind to patients between prenatal appointments, and enhance the overall prenatal experience of pregnant women.

To evaluate the functionality and acceptability of HeraBEATTM we plan to:

- 1. Assess the functionality of HeraBEAT™ self-administered by pregnant women.
  - a. Hypothesis: Pregnant women will demonstrate a working knowledge on use of the device, when observed by medical staff, will trouble-shoot appropriately and will rate the device instructions as easy to follow.
  - b. Hypothesis: Pregnant women will appropriately self-monitor FHR successfully at home, transmit the data to caregivers, and use the device as prescribed.
- 2. Assess the acceptability of HeraBEATTM when self-administered by a pregnant women in the home by assessing the following
  - a. Hypothesis: Pregnant women will rate the device as easy to use, easy to interpret, and have minimal disruption in lifestyle as measured by a standardized survey.

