# 5.0 Study Methods

# 5.1 Overview

Primary Objective

- 1) To evaluate the functionality of HeraBEAT™ when self-administered by pregnant women by assessing the following:
  - a) Study participants' independent use of the device assessed by study personnel observation, including ability of participants to read and follow HeraBEATTM device instructions, and find fetal heart rate without assistance evaluated using the HeraBEATTM Independent Device Assessment Form. (*Appendix C*).
  - b) Data transmission from the device to the healthcare provider via a HIPAA compliant cloud-based server, assessed by evaluating the data transmitted to the healthcare provider from the HeraBEAT™ US device, including subject' success in finding FHR, time to find FHR, frequency of use, and clinical utility of the FHR/MHR data (*Appendix B*).

Secondary Objective

- 1) To evaluate the acceptability of HeraBEAT™ when self-administered by a pregnant women in the home by assessing the following:
  - a) Patient usability and ease of use assessment as measured by the System Usability Scale (SUS), *Appendix D*.
  - b) Impact on utilization of care as measured by urgent triage and/or emergency care visits for concerns regarding fetal well-being.

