## 8.2 Sample Size

Difference in ease of use between our standard fetal Doppler and HeraBEAT™ device, as measured by the System Usability Survey (SUS) will be the primary outcome. Approximately 1500 – 2000 expectant mothers receive prenatal care in the obstetric department annually. We aim to recruit 50 participants (50 per arm, with cross-over) for a 99.7% power to detect a 10-point difference in SUS, as this accounts for a withdraw / post-randomization exclusion, estimated as high as 10% (assuming a proportion of expectant mothers to withdraw participation after being enrolled or found to not meet criteria after the fact).

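### McNemar's test on the FHR flag compares only how often each method flags, so it cannot show the association between device and clinic that section 8.0 asks of it

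*Combined protocol and SAP*

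**What the plan says.** Section 8.0 (Data Analysis Plan) defines the variable: "Clinical concerns in FHR will be indicated as a FHR less than 110 bpm or greater than 160 bpm". The next sentence assigns the test: "These data will be analyzed as McNemar's test on the association of the study medical devices with the clinical standard of care".

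The paired readings appear to come from section 5.6 (Schema), where women using HeraBEAT bring the device to appointments "for comparison of MHR and FHR during their routine clinic appointments using methods documented in" Appendix E. That appendix is not in the text available for this review. For the other device, section 5.6 describes only home recording: "Patients using the standard handheld Doppler device will be given a study brochure for recording their weekly data".

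The other provision in section 8.0 that could reach FHR is the set of ad-hoc tests, "with each outcome compared between study arms using t-tests for continuous outcomes and chi-square tests for dichotomous outcomes". Those compare study arms with each other, not device with clinic.

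Two statements elsewhere give the comparison its purpose. Section 1.0 proposes that home use "will result in accurate monitoring of fetal heart rate". This is a general proposition and not one of the numbered hypotheses. Section 5.1 lists "frequency of use, and clinical utility of the FHR/MHR data" within primary objective 1b. Section 8.2 says that ease of use "as measured by the System Usability Survey (SUS) will be the primary outcome".

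**The concern.** Association, or agreement, between a device and clinic care is a question about individual readings: when the clinic reading is out of range, is the device reading out of range too? McNemar's test does not address that. It tests marginal homogeneity, meaning that the two methods flag equally often overall. Two methods can flag equally often and never flag the same reading. They can also be closely associated and still flag at different rates.

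The risk lies in interpretation. A non-significant result is easily read as the device matching the clinic, and from there as support for accurate monitoring or for the clinical utility named in objective 1b. The plan does not say it will be read that way. But nothing else in the available text would show that the reading was wrong.

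**Working it through.** **Inputs.** The flag and the test are from section 8.0. Section 8.2 gives 50 participants in a crossover and allows for up to 10% withdrawal or exclusion: 50 x 0.90 = 45. I use one device-clinic pair per woman. The documents give no flag rate, discordance rate or design figure for this analysis, so there is no stated figure to reproduce. The tables below are illustrations and not predictions.

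**Notation.** a = flagged by both; b = clinic only; c = device only; d = neither; n = a + b + c + d.

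**Formulas.**
- Exact McNemar: two-sided binomial test of b out of b + c against 1/2. Cells a and d do not enter. With b + c = 0, p is taken as 1.0.
- Kappa = (po - pe)/(1 - pe), where po = (a + d)/n and pe = [(a + b)(a + c) + (c + d)(b + d)]/n².
- Fisher's exact test on the same table, as a test of association.

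**Equal margins.** With 5 flags per method in 45, pe = (5 x 5 + 40 x 40)/45² = 1625/2025 = 0.802 in each of the first four rows.

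| (a, b, c, d) | po | McNemar p | kappa | Fisher p |
|---|---|---|---|---|
| (5, 0, 0, 40) | 45/45 | 1.0 | 1.00 | 8.2e-7 |
| (3, 2, 2, 38) | 41/45 | 1.0 | 0.55 | 0.0065 |
| (1, 4, 4, 36) | 37/45 | 1.0 | 0.10 | 0.46 |
| (0, 5, 5, 35) | 35/45 | 1.0 | -0.125 | 1.0 |
| (10, 6, 0, 29) | 39/45 | 0.031 | 0.68 | 2.5e-6 |

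Worked example for the fourth row: kappa = (0.778 - 0.802)/(1 - 0.802) = -0.125. The device misses every reading that the clinic flagged, and McNemar's p is the same as for a perfect device.

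**Unequal margins.** In the fifth row, p = 2 x (1/2)⁶ = 0.031. The test rejects although the association is strong.

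**What agreement measures would show** (Clopper-Pearson 95% CI, clinic as reference):
- (5, 0, 0, 40): positive agreement 5/5, 48% to 100%; negative agreement 40/40, 91% to 100%.
- (0, 5, 5, 35): positive 0/5, 0% to 52%; negative 35/40, 73% to 96%.
- (10, 6, 0, 29): positive 10/16, 35% to 85%; negative 29/29, 88% to 100%.

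The two tables that McNemar's test cannot tell apart are clearly separated.

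**Why bpm differences are needed as well.** Suppose clinic readings all lay between 115 and 139 bpm (assumed) and the device read 20 bpm high throughout. It would show 135 to 159 bpm. Neither method flags anything, and McNemar's p is 1.0 despite a 20 bpm error.

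**Precision of the bpm analysis with 45 single pairs,** in units of the SD of the differences:
- Mean difference: 1.96 x sqrt(1/45) = 0.29 SD.
- Each limit of agreement: 1.96 x sqrt(1/45 + 1.96²/(2 x 44)) = 0.50 SD.

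**The case against.** **Association may be loose wording for comparison.** If the question is whether the device systematically flags more or less often than the clinic, McNemar's test is a proper paired test. That stands as a defence of the test for that purpose, and it is why the test can be kept. The wording would still need correcting, and section 8.0 would still contain no measure of agreement for the comparison that section 5.6 schedules.

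**Appendix E may already specify agreement statistics.** It may. It was not available, so I make no claim that the unit of analysis, the handling of maternal heart rate (MHR) or any Doppler-clinic pairing is undefined. Section 8.0 does not refer to Appendix E, and the purpose it gives McNemar's test would be wrong whatever the appendix says.

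**The harm is hypothetical and not primary.** No section treats a non-significant McNemar result as proof of accuracy, accuracy is not a numbered hypothesis, and the SUS outcome is untouched. Section 5.7 adds that home data alone will not decide care. All of this is right and limits the severity.

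**The illustrative flag rates have no source.** One method flags 11% (5/45) in the first four tables and 36% (16/45) in the last, in a low-risk cohort. The tables do not predict what the trial will see. The central point does not depend on the rate, because cells a and d never enter the test.

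**Agreement may be imprecise.** With one clinic flag, 1/1 has a 95% CI of 2.5% to 100%; with none, positive agreement is undefined. That is a real limit of the flag, and a further reason to analyse the bpm values.

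**Conclusion.** The concern holds. As section 8.0 is written, its device-versus-clinic analysis cannot answer the question it poses. With equal flag counts it returns p = 1.0 while kappa runs from -0.125 to 1.00, and it can give p = 0.031 when kappa is 0.68.

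The statistical point follows from the form of the test and needs no assumption about flag rates. The figures assume 45 single pairs and the flag counts shown. I make no power claim, because the documents give no discordance rate. The statement that no other device-versus-clinic analysis is planned covers only the text available, without Appendix E.

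This should be corrected before analysis, but it does not threaten the primary SUS comparison.

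**What to change.** Amend section 8.0 as follows.

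1. Make agreement the main analysis of the HeraBEAT-clinic comparison in section 5.6. For the 110/160 bpm flag, report the 2x2 table with positive and negative percent agreement and 95% CIs.
2. Report the mean difference and 95% limits of agreement in bpm for FHR and MHR, since section 5.6 compares both and the flag discards the size of any difference.
3. Account for clustering by woman if she contributes more than one visit.
4. Keep McNemar's test, if wanted, as a labelled check for systematic over- or under-flagging, and replace the word association accordingly. State that a non-significant result is not evidence of agreement.
5. Limit the claim to HeraBEAT unless Appendix E defines paired Doppler-clinic readings.
6. If Appendix E already specifies any of these analyses, cite it in section 8.0.

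**Cost.** This is SAP wording and slightly more analysis, using a comparison already scheduled. It assumes that paired numeric readings are recorded, which Appendix E would confirm. The drawback is that positive agreement will be imprecise if few readings are out of range: even 5/5 gives 48% to 100%.

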  - b. Hypothesis: The intervention will reduce the rate of healthcare utilization without impacting maternal safety or the process of care standards specified by the American College of Obstetricians and Gynecologists (ACOG).

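### Utilisation, a stated secondary objective, has no analysis that fits the crossover: the only applicable rule compares study arms, and no rule assigns a visit to a device

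*Combined protocol and SAP*

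**What the plan says.** Section 5.1 lists as secondary objective 1b "Impact on utilization of care as measured by urgent triage and/or emergency care visits for concerns regarding fetal well-being". Hypothesis 2b in 1.0 is directional: "The intervention will reduce the rate of healthcare utilization without impacting maternal safety". It names no comparator.

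Sections 5.2 and 5.6 describe a randomised crossover. Women monitor "once weekly, using their assigned device, from 20 weeks to 36/37 weeks gestation", changing device after about 8 weeks. Section 5.8 collects chart data, including utilisation, from enrolment to the postpartum appointment at 6–8 weeks. Section 5.9.3 lists clinic visits, triage visits and hospitalisations, with a clause about being prompted by home monitoring that may qualify all three or only the last.

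In 8.0, the intention-to-treat sentence analyses women by randomisation: "including all mothers randomized to the study in the arm to which they were randomized". SUS receives crossover handling: "analyzed as a two sample t-test prior to cross over", then an order-adjusted or paired analysis. Abnormal fetal heart rate receives McNemar's test. Utilisation is not mentioned. Only two sentences reach it: "Additional ad-hoc analysis will be performed using standard techniques appropriate for randomized trials, with each outcome compared between study arms using t-tests", and the baseline-adjustment sentence, which calls for "ANCOVA or regression models which include an indicator for study arm".

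Section 8.2 uses arm differently: "We aim to recruit 50 participants (50 per arm, with cross-over". With 50 women in total, 50 per arm works only if arm means device.

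**The concern.** Every woman is meant to use both devices, so an arm comparison needs a definition of arm and a rule for which visits count. The plan supplies these for SUS and not for utilisation. Three readings are open:

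1. Arm is the randomised order, with whole-study counts. This contrasts sequences, not devices.
2. Period 1 only. This is a valid device comparison that discards half the data.
3. Arm is the device, as in 8.2. Unpaired tests are then applied to two counts from the same women, with no period term.

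The readings can answer hypothesis 2b differently from the same data. The collection window also includes time on neither device, and no text says how to treat those visits.

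**Working it through.** **Plan's own figure.** There is none for utilisation. The 99.7% power in 8.2 concerns SUS and comes without an SD.

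**Expected contrast by order.** Let d and h be mean visits per 8-week period on the standard Doppler and on HeraBEAT, and let later-period rates be k times earlier ones.

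- HeraBEAT first: h + kd. Doppler first: d + kh.
- Difference: h + kd − d − kh = (d−h)(k−1).
- If d > h, this is 0 at k=1, positive (HeraBEAT looks worse) at k>1, and negative (right direction, distorted size) at k<1.

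Without carry-over, visits outside the device periods have the same expectation in both orders and only add noise.

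**Within-woman comparison.** Period 1 minus period 2 has mean h − kd (HeraBEAT first) and d − kh (Doppler first). Half the difference is (h−d)(1+k)/2, the device effect averaged over periods.

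**Illustration, assumed d=0.4, h=0.2, k=2.**

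- Totals by order: (0.2+0.8) − (0.4+0.4) = +0.20.
- Period 1: 0.2 − 0.4 = −0.20.
- By device: (−0.2 − 0.4)/2 = −0.30.

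At k=0.5, totals by order give 0.2 × (−0.5) = −0.10, against a device effect of −0.2 × 1.5/2 = −0.15.

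**How often this shows.** Simulation: 20,000 trials per scenario, Poisson counts, two-sided 5% (assumed), 45 women split 23/22 (50 less the 10% loss in 8.2). Rates are assumptions throughout.

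Totals by order:

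- k=1: rejection 4.4–5.1%, although HeraBEAT truly halves visits.
- 0.4 v 0.2 at k=1.25, 1.5 and 2: expected difference +0.05, +0.10 and +0.20 visits; rejection 5.1%, 6.6% and 10.6%; significant in the wrong direction 3.7%, 5.8% and 10.3%.

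Power of the other tests at k=1:

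| Doppler v HeraBEAT rate | Between-woman variation | Period 1 only | Unpaired by device | Within-woman, period-adjusted |
|---|---|---|---|---|
| 0.2 v 0.1 | none | 12% | 23% | 22% |
| 0.4 v 0.2 | none | 22% | 40% | 39% |
| 1.0 v 0.5 | none | 47% | 78% | 77% |
| 0.2 v 0.1 | gamma, variance 1 | 11% | 18% | 20% |
| 0.4 v 0.2 | gamma, variance 1 | 17% | 30% | 38% |
| 1.0 v 0.5 | gamma, variance 1 | 28% | 54% | 74% |

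With no device difference, rate 1.0 and variance 1, the unpaired test rejects 0.7% of the time, so its intervals are too wide. The within-woman test rejects 4.3–5.4% across the null scenarios.

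**Device-free antenatal time**, assuming delivery at 40 weeks: (20 − enrolment week) + (40 − 36 or 37). Table 2 places consent at 18–20 weeks, giving from 3 of 20 weeks (15%) to 6 of 22 weeks (27%). Only enrolment at 12 weeks gives up to 8 + 4 = 12 of 28 weeks (43%).

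**The case against.** A reader might infer that the plan will reverse the utilisation result. The documents do not support that. No section prescribes whole-study totals; the window in 5.8 governs all chart abstraction and is not stated as the utilisation analysis window; 8.2 uses arm to mean device; and the generic sentence covers additional work by techniques suited to randomised trials. A reversal needs the order reading together with visit rates that rise, and no rates are given. Even then a significant wrong-direction result is uncommon, about 4–10% in the scenarios above. This stands: the likely harm on that reading is an uninformative null.

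On the device reading, nothing is lost if women share one visit rate; the loss depends on assumed variation between women. This also stands. A 43% device-free share would be too strong, because it needs enrolment at 12 weeks. If the home-monitoring clause in 5.9.3 covers every visit type, most device-free visits drop out.

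Section 8.0 also says that the statistician and analysts are blinded to arm. That limits a result-driven choice among readings but does not settle which applies. Utilisation is secondary and unpowered in a 50-woman usability study, which bears on severity and not on the omission.

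**Conclusion.** The point holds with modest severity. That utilisation has no named analysis and no attribution rule is plain from the text. The contrast (d−h)(k−1) on the order reading is algebra and needs no assumed rate beyond a common k and no carry-over. The power figures are illustrations only.

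The plan does not say which reading applies: one cannot see a device effect when rates are stable, one uses half the data, and one ignores pairing. A better analysis is available from data largely collected already. Since both periods involve home monitoring, the trial can estimate only HeraBEAT against the standard home Doppler. A reader might take hypothesis 2b as a claim about home monitoring against none; the design does not support that. The SUS and fetal heart rate analyses are unaffected.

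**What to change.** In 8.0, replace the between-arms rule for utilisation with wording such as:

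> Visits meeting objective 1b will be assigned by date to device period 1 or 2, with the actual crossover date as boundary, and to the device allocated for that period under the randomised order, in keeping with intention to treat. Visits outside the device periods will be described separately. Each woman's period-1 minus period-2 difference in visits per week will be compared between the two orders by two-sample t-test; half the HeraBEAT-first minus Doppler-first difference in means is the period-adjusted device effect, reported with a 95% CI. A Poisson GEE clustered by woman (device, period, log-weeks offset, small-sample standard errors) will be reported alongside, so that women with one period or a short period are included.

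Also state hypothesis 2b relative to the standard home Doppler, define arm once and use it consistently in 8.0 and 8.2, and reconcile the endpoint in 5.1 (urgent triage and emergency visits) with the list in 5.9.3, which does not name emergency visits.

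The cost is SAP wording and one derived variable: visit dates come from the chart and the crossover date from device return (5.6). Reconciling the endpoint may add some abstraction. There are downsides:

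- The t-test drops one-period women, who may include those discontinued after a high-risk diagnosis (7.0).
- It loses power with short periods. If 20% of women had a second period of 0.5–3 weeks (an assumption), power falls from 40% to 33% for 0.4 v 0.2 and from 77% to 64% for 1.0 v 0.5.
- The GEE is conservative when visits are rare: 1.2% null rejection at 0.1 visits per period.
- Carry-over is assumed absent.
- Power stays modest at low rates: about 20% for 0.2 v 0.1 and about 39% for 0.4 v 0.2.
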